1. Prior to the start of the study, all study nurses/clinicians will receive training on how to use the test devices. Clinical decisions will still be based on the standard of care, which will not be interrupted during the study. The study nurse/clinician will apply the temperature sensors to the infant.
2. A research technician will be available for the duration of the study to record the data from the monitors.

Enrollment :

Enrollment will take place after fully informed and written consent from the parent or guardian. A parent will be free to withdraw their child from participating at any time, without explanation and without detriment to ongoing care. There will be no financial benefit to participants though the infants will benefit from close monitoring. A participant identification number will be assigned. This number will be used for identification purposes throughout the study.

Monitoring of Neonates:

During the trial, the following steps will be taken:

A trained study nurse will assess the subject for clinical complications before attaching the temperature monitoring device.

- 1) A trained study nurse or clinician will attach the three test temperature monitoring devices to the infant. A trained research assistant from Rice University or from the Biomedical Engineering Department at Malawi Polytechnic will observe all procedures and will notify the nurse of any observed errors so they may be corrected. They will also be able to answer any technical questions from the nurse.
- 2) The trained study nurse will attach the temperature probe from the commercial gold standard as well as provide any other care needed.
- 3) A research assistant will use a laptop to collect data from the continuous temperature monitors (NTM and gold standard). The nurse will record the temperature readings every hour from all monitors on paper forms along with the standard of care.
- 4) Each time an alarm sounds from any device (Bempu and the commercial gold standard have audible alarms), the nurse will record all temperature values including a reading taken with the standard of care method. If the subject is found to be hyper/hypothermic, the nurse will respond with the appropriate standard of care.
- 5) Temperature monitoring will continue for up to 3 days. The research assistant may ask the nurse to remove and reapply the temperature probes during this period.

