The accuracy of the temperature sensors will be determined by calculating the difference between the temperatures recorded by the temperature sensor and the commercial patient monitor at each point in time. The average error between the temperature sensor and the gold standard will be calculated for each subject and compiled in a Bland-Altman plot. The 95% limits of agreement will be calculated. Our target error is less than +/- 0.5 C.

For the devices that do not provide a continuous numerical reading, the recorded state every hour will be compared to the gold standard at that point in time. The sensitivity and specificity for hypo/hyperthermia will be calculated for each device.

The ability of each device to accurately diagnose hypothermia will also be calculated with respect to the alarm events for each device for which they were recorded. The sensitivity and specificity will be determined using the number of false alarms collected during the study.

As a secondary analysis, the errors will be plotted against thermal treatment type and ambient temperature to determine their confounding effects on accuracy. An ANOVA will be used to determine statistical significance.

The research team from Rice University and QECH will be responsible for all data analysis. We plan to analyze data using Excel, MATLAB, and associated statistics packages.

[viii] Results Presentation

Statistical analysis will be performed and means, limits of agreement, sensitivities and specificities will be reported. Tables and graphs may also be used to present any additional correlations, explain outliers, or demonstrate confounding effects.

[ix] Dissemination of Results

The results of this study will be made available to the Ministry of Health, COMREC, the College of Medicine Library, the Department of Paediatrics, and other partners working in neonatal and child health. A copy of the final report and any published papers or abstracts will be submitted to The Health Sciences Research Committee and the University Research and Publication Committee (URPC) through the COMREC Secretariat. Findings will be published in academic journals and conference

proceedings in an effort to disseminate results to potential end-users. The research findings of this study will be critical in the evaluation of future interventions.

I. Ethical considerations

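### Probes may be removed and reapplied during monitoring, but no rule covers off-body or warm-up readings, so these can enter the alarm and hypothermia-detection results as device errors or false hypothermia

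*Combined protocol and SAP*

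**What the plan says.** Section H [vi], Monitoring of Neonates, step 5 sets the duration, "Temperature monitoring will continue for up to 3 days", and continues: "The research assistant may ask the nurse to remove and reapply the temperature probes during this period". It does not say how often, for how long or for which probes, and it does not ask for the times to be recorded. The same section lets the nurse take off one test device and carry on with the others. NTM and the gold standard are logged by laptop (step 3), and their alarms are captured automatically (Intended Data Collection, item 2a). The NTM low-temperature light is triggered below 36.5 °C (section E).

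Section H [vii] obtains accuracy by "calculating the difference between the temperatures recorded by the temperature sensor and the commercial patient monitor at each point in time". It then states: "The average error between the temperature sensor and the gold standard will be calculated for each subject and compiled in a Bland-Altman plot". Limits of agreement follow, with the criterion "Our target error is less than +/- 0.5 C". Devices without a continuous numerical reading are compared with the gold standard by their hourly state. For alarm events: "The sensitivity and specificity will be determined using the number of false alarms collected during the study".

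The protocol contains no equilibration period, no definition of when valid data begin, and no exclusion of readings or alarms that arise while a probe is off the infant.

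**The concern.** A sensor taken off the skin drifts toward room temperature, and after reapplication it needs some minutes to climb back. During that time it reads below 36.5 °C in an infant who is not cold. The plan gives the analyst no basis for setting these readings aside, and the effect depends on which probe is cold:

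- **Test device cold, reference on skin:** the readings count as negative device error and as a false alarm, and specificity falls.
- **Reference cold, test device on skin:** the reference shows hypothermia that is not there. A correct test device is scored as having missed it, and sensitivity falls.
- **Both cold together:** the errors partly cancel, but the two can agree on a hypothermic episode that never happened.

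The bias can therefore run either way. Objectives 1a and 1c (section G) are continuous measurements and temperature during alarm events, so the exposed results are core outputs. Removal times that are not written down when they occur cannot be recovered reliably from the traces.

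**Working it through.** The documents give no sensor time constant, SD, sampling interval or removal frequency, so there is no stated figure to reproduce. What follows is an illustration.

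**From the documents:** monitoring of at most 72 h; low threshold 36.5 °C; target ±0.5 °C; up to 60 infants.

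**Assumed:** on-body error SD 0.20 °C; true temperature 36.8 °C; sensor starts d = 3 to 6 °C below skin; time constant τ = 2 to 5 min; 1-minute sampling (N = 72 × 60 = 4,320); the other sensor at skin temperature; the same event in every infant.

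**1. Time spent below 36.5 °C.** Warm-up error is d·exp(−t/τ). It stays larger than 36.8 − 36.5 = 0.3 °C for τ·ln(d/0.3) minutes:
- τ = 2: 2·ln(10) = 4.6 to 2·ln(20) = 6.0 min
- τ = 5: 5·ln(10) = 11.5 to 5·ln(20) = 15.0 min

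Each application therefore gives about 5 to 15 min of spurious low readings.

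**2. Per-subject mean, the unit in the Bland-Altman plot.** One warm-up sums to d/(1 − exp(−1/τ)). The largest case (d = 6, τ = 5) is 33.1 °C·min, and 33.1/4,320 = 0.008 °C. Five off-body minutes at full offset add 5 × 6 = 30, giving 63.1/4,320 = 0.015 °C. Two such events give 0.029 °C. One such event in only 24 h gives 63.1/1,440 = 0.044 °C.

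**3. Pooled point-level limits.** Limits = 1.96·√(0.04 + S/N), where S is the sum of squared artefact errors. With no artefact, 1.96 × 0.20 = ±0.39.

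| One event | S, d = 3, τ = 2 | S, d = 6, τ = 5 | Limits, 72 h | Limits, 24 h |
|---|---|---|---|---|
| Warm-up only | 14.2 | 109.2 | ±0.41 to ±0.50 | ±0.44 to ±0.67 |
| Plus 5 min off body | 59.2 | 289.2 | ±0.45 to ±0.64 | ±0.56 to ±0.96 |

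For example, 1.96·√(0.04 + 109.2/4,320) = 0.50. Two events in 72 h give ±0.42 to ±0.59, or ±0.51 to ±0.82 with off-body time.

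**4. Wider assumptions.** With ambient temperature 25 to 30 °C and 5 to 10 off-body minutes, one removal in 72 h shifts the mean by −0.01 to −0.03 °C. The pooled limits then run from −0.49/+0.47 to −1.10/+1.05 °C. The size depends heavily on inputs that the documents do not give.

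**5. Alarms.** Suppose an NTM record holds 5 true alarms and 1 false one. The share of alarms that are true is 5/6 = 0.83. One removal alarm makes it 5/7 = 0.71, and three make it 5/9 = 0.56. A few events matter here because there are few alarms to dilute them.

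**6. Hourly states.** One contaminated reading among 72 gives specificity 71/72 = 0.986, a small effect.

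**The case against.** The strongest reply is that the planned agreement statistic is barely touched. Section H [vii] averages the differences within each infant before plotting, and a shift of 0.03 °C is small beside a 0.5 °C target. A reader might infer from the widened limits above that the Bland-Altman result would miss its target because of the procedure. The documents do not support that: those limits describe pooled point-level differences, a summary the section does not state. This part of the objection stands.

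It also stands that removal is permitted and not scheduled. A reader might multiply one initial application and one reapplication by 60 infants to reach 120 spurious episodes per monitor. That is a ceiling. It needs full enrolment, a reapplication in every infant, and logging already running at first attachment, whereas attachment is listed before laptop collection.

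A reader might further infer that the plan orders off-body data to be included, or that the team, part of which developed NTM, will trim inconvenient readings. The documents show neither. They are silent on artefacts, and that silence leaves any later cleaning to discretion.

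There are partial safeguards. The nurse takes a standard-of-care reading when an alarm sounds, a research assistant observes procedures, and fit and movement are recorded. These could help to identify some probe-off alarms, but none is linked to an analysis rule, and the NTM alert is described as a light, not a sound. They reduce the problem without closing it.

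**Conclusion.** The concern holds in a limited form. The plan allows removal and reapplication while data are being logged, and it has neither a logging requirement nor a rule for off-body and warm-up periods. The results at risk are alarm-based accuracy, hypothermia sensitivity and specificity, and any point-level summary of the continuous data. The per-subject mean error is essentially unaffected with one or two events in a 72 h recording; shorter recordings or more frequent removal would weaken that reassurance.

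All the sizes rest on assumed SD, temperature gap, time constant and sampling interval, and on the other sensor being at skin temperature. Reapplication frequency is unknown, so the total effect on the study cannot be calculated. The change is still worth making before data collection, because missing removal times cannot be reliably reconstructed afterwards.

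**What to change.** 1. Add to the monitoring form a time stamp for every application, removal and reapplication of each device, including the gold standard.
2. Before any paired differences are examined, fix a stabilisation rule. For NTM and the gold standard it can be a fixed window or depend on the sensor's own trace, for example a change of less than 0.1 °C over 5 minutes. A trace rule must start from the recorded reapplication time, since a probe lying at room temperature is also stable. For Bempu and ThermoSpot, which have no logged trace, use a fixed time window.
3. From removal until that window ends, exclude readings and alarms from the accuracy, sensitivity/specificity and false-alarm analyses. Drop a comparison if either the test device or the reference is affected. Apply the same rule to the initial application.
4. Report excluded time per device, and a sensitivity analysis with nothing excluded.

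The cost is a few minutes of data per application and slightly more recording. Clinical care is unchanged.

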A. Title

Assessment of low-cost temperature monitoring tools for neonates.

B. Investigators

Principal Investigator: [name], College of Medicine, Blantyre, Malawi

Co-Investigators: [name], Dept. of Bioengineering, Rice University, Houston, TX USA
[name], Dept. of Bioengineering, Rice University, Houston, TX, USA
[name], Rice 360: Institute for Global Health, Rice University, Houston TX, USA
[name], Rice 360: Institute for Global Health, Rice University, Houston TX, USA
[name], Rice 360: Institute for Global Health

Investigators' CVs: Please see Appendix 1

C. Institutions under whose umbrella the research project will be conducted

- [i] College of Medicine, Blantyre, Malawi
- [ii] Rice University, Houston, TX, USA

D. Executive summary

Problem statement: Neonatal hypothermia is a pervasive global challenge; as many as 85% of infants born in hospitals in low-resource settings are too cold (defined as a temperature <36.5C) [1]. A recent study of 23,240 newborns in Nepal showed that babies with moderate hypothermia are nearly five times more likely to die than normothermic infants; the risk of death is more than 23 times higher for babies with severe hypothermia [2]. While the risks of being too cold are well recognized, hypothermia remains a largely invisible problem in overcrowded newborn units in low-resource settings. Electronic temperature monitors used in high resource settings are not available in low-resource settings because they are too costly or require a constant supply of consumable thermistors. Simple digital or analog thermometers are often unavailable; when they are available, wards are often too short-staffed to permit routine monitoring at regular intervals.

Aim of Study: A team of researchers at Rice University and QECH are working to develop a low-cost temperature sensor that can continuously monitor an infant's temperature (NTM). This robust, low-cost device will allow for the individualized monitoring of each infant with alerts for hypo and hyperthermia. A reusable band to

hold the temperature sensor will eliminate disposable components. This study will assess the accuracy of this novel device against a gold standard along with existing low cost temperature monitors, ThermoSpot and Bempu, to determine which tool is most accurate and effective for neonatal wards.

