[iii] Study Population

Subjects will be drawn from the population of infants being treated at QECH.

[iv] Study Period

We anticipate the study will take 2-3 months.

[v] Sample Size

This study will enroll up to 60 infants at Queen Elizabeth Central Hospital. Up to 30 subjects will be collected from the neonatal ward and 30 subjects from the KMC ward. This sample size will ensure that we are able to collect sufficient data from infants with a range of gestational ages, weights, temperatures, and treatment locations (ie open cot, radiant warmer). The data from this study can be used to calculate the sample size needed in a larger study to evaluate changes in outcomes and nurse behavior related to the different temperature monitors.

Inclusion criteria:

1. The subject is currently being treated at QECH in the neonatal or KMC ward.
2. Study devices are available for use.
3. The subject's caregiver has provided informed consent for their child to participate.

The subject may be excluded from the study at the clinician's discretion for any reason including potential for skin irritation, cough or other condition that may preclude use of the temperature belt, or concurrent treatments that may require increased patient care.

If a patient is not enrolled in the study, the patient will receive the standard of care.

Informed Consent:

The investigator will provide details of the study to all eligible subjects' guardian and answer all questions. Fully informed and signed consents will be obtained from the subject's guardian prior to the start of any study procedures.

Documentation of the consent process will include the following elements:

- Date and time of consent;
- Topics discussed with the subject's guardian (e.g. risk, benefits, etc.); and
- Confirmation that the consent was reviewed, that the guardian's questions were answered, and that a signed copy of the consent was provided to the subject's guardian.

Potential Benefits and Compensation of the Proposed Research to Human Subjects and Others: Neonates and infants at risk for hypothermia may benefit from participating in this study as alternative forms of accurate and frequent monitoring may not be readily available. This study may benefit infants in the future as the accuracy and usability of the test devices can be used to improve access to temperature monitoring equipment in the future.

[vi] Data Collection

Training:

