A research assistant will be available during the trial to mitigate any complications with the devices. If the subject's guardian, the nurse, or the research assistant indicates concern during the tests, temperature monitoring will be discontinued and the subject's treatment will return to the standard of care. The nurse can choose to remove one of the test devices and continue the study with the remaining monitors if any issue arises.

Clinical data will be collected on paper forms as is consistent with current clinical practice. Data from the temperature monitors will be saved on a secure study server for analysis. Clinical and/or research personnel will record information, excluding personal identifiers, on a standardized patient monitoring form. After the subject's participation is complete, a research assistant will collect and scan the form.

The following section details the variables that will be measured or calculated in the study.

Intended Data Collection:

1. Baseline demographic and relevant medical information
 - a. Recorded once at enrollment
 - i. Date of Study
 - ii. Date of Birth
 - iii. Sex
 - iv. Birth Weight
 - v. Type of delivery
 - vi. Gestational age at birth
 - vii. Corrected gestational age
 - viii. Abdominal circumference
 - ix. Admission Temperature
 - b. Recorded throughout study as clinically collected
 - i. Other comorbidities
 - ii. Medications/treatments given
 - iii. Current weight
 - iv. Additional temperature measurements taken as standard of care
2. Accuracy
 - a. Recorded automatically by study equipment
 - i. Abdominal temperature and alarms from Rice designed temperature monitor and gold standard device
 - b. Recorded every hour by study nurse or as alarm events occur
 - i. Temperature measurements from other devices
 - ii. Temperature measurements using standard of care method (axillary)
 - iii. Ambient temperature
 - iv. Current thermal treatment, if any
 - c. Movement/other caregiving
 - d. Fit/tightness of the devices

A log of observed user error and comments may be used to improve the usability of the test devices.

[vii] Data Management and Analysis

Personal identifiers will be removed from the data which will be kept on a secure server accessible only to study personnel.

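### Single-device removal may leave the three tools compared on different infant-hours, and the plan has no matched comparison and no removal record

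*Combined protocol and SAP*

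**What the plan says.** The Aim of Study in section D is "to determine which tool is most accurate and effective for neonatal wards", and section F also promises a comparison of the three solutions. Section H [i] calls the study a pilot comparison of each monitor with a commercial gold standard.

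On data collection, section H [v] states: "This study will enroll up to 60 infants at Queen Elizabeth Central Hospital". Section H [vi] adds: "Temperature monitoring will continue for up to 3 days". All devices sit on the same infant and are read together: "The nurse will record the temperature readings every hour from all monitors on paper forms along with the standard of care". The same section then allows asymmetric follow-up: "The nurse can choose to remove one of the test devices and continue the study with the remaining monitors if any issue arises". It also lets probes be taken off and reapplied during monitoring.

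On analysis, section H [vii] states: "The sensitivity and specificity for hypo/hyperthermia will be calculated for each device". Alarm performance is assessed "with respect to the alarm events for each device for which they were recorded". For numerical agreement, "The average error between the temperature sensor and the gold standard will be calculated for each subject and compiled in a Bland-Altman plot".

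No sentence restricts a comparison to hours that devices have in common, or says how hours without a device are handled. The list of intended data in section H [vi] includes fit and movement, but not the removal of a device, its time or its reason. The nearest item is a log of user errors and comments, which may be used to improve usability.

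**The concern.** Readings are paired by design: same infant, same hour, same reference. The analysis does not use the pairing. Each device gets its own sensitivity and specificity on its own set of hours. If one device comes off some infants while the others stay on, a difference between two devices mixes a difference in accuracy with a difference in the hours observed.

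The comparison of tools is part of the stated aim, so this could affect the answer that readers take from the study. Removals also bear on whether a device is practical on the ward, which is a second purpose in section G. The plan does not specify that they be recorded or reported, and reasons that were not noted at the time are hard to recover.

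**Working it through.** The documents give no removal rate, no sensitivity and no share of hours that are difficult to measure. There is therefore no stated figure to reproduce, and every value below except the maximum exposure is an assumption.

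**Exposure.** Up to 60 infants for up to 72 hours gives at most 60 × 72 = 4,320 infant-hours per device. The hours in which a device was actually worn are unknown.

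**Model.** Take two devices with identical true accuracy. Among hypothermic hours, a share h is difficult. Sensitivity is 0.90 in easy hours and 0.60 in difficult ones. Device A is off for a fraction q of the difficult hours; device B stays on throughout.

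- B: (1 − h) × 0.90 + h × 0.60
- A: [(1 − h) × 0.90 + h(1 − q) × 0.60] / (1 − hq)

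**Removal in difficult hours, q = 0.5.**

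- h = 0.5: B = 0.45 + 0.30 = 0.75. A = (0.45 + 0.15) / 0.75 = 0.80. False advantage to A: 5 points, with 0.5 × 0.5 = 25% of A's hypothermic hours lost.
- h = 0.2: B = 0.72 + 0.12 = 0.84. A = (0.72 + 0.06) / 0.90 = 0.867. False advantage to A: 2.7 points, with 0.2 × 0.5 = 10% of hours lost.

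**Other assumed values, still q = 0.5.**

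- Difficult-hour sensitivity 0.70, h = 0.1: 0.889 against 0.88, about 1 point.
- Difficult-hour sensitivity 0.70, h = 0.3: 0.865 against 0.84, 2.5 points.
- Difficult-hour sensitivity 0.50, h = 0.5: 0.767 against 0.70, about 7 points.

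**Removal unrelated to difficulty.** If A loses the same fraction of easy and difficult hours, the fraction cancels. With h = 0.5 and 25% of each lost, A = (0.375 × 0.90 + 0.375 × 0.60) / 0.75 = 0.75, equal to B. If sensitivity is the same in both kinds of hour, there is again no difference.

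**Removal in easy hours.** With h = 0.5 and half of the easy hours lost, A = (0.25 × 0.90 + 0.50 × 0.60) / 0.75 = 0.70 against 0.75. The sign reverses.

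**After matching.** In the first case, limiting both devices to hours when both were worn gives 0.80 for each, so the false difference is zero. But 0.80 is not the 0.75 that applies to all hours. Matching corrects the comparison between devices; it does not recover the performance of either in the hours lost. That is why the all-hours results and a count of removals must stand beside it.

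**The case against.** Four objections have force.

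- **No ranking is planned.** Section H [vii] assesses each device against the gold standard and plans no between-device test. This stands, but sections D and F promise a comparison, and separate results set side by side will be read as one.
- **The reason for removal is not given.** A reader might infer that a device comes off in its worst hours and so looks better than it is. The documents do not support this. Section H [vi] says only that an issue arises. Fit is a recorded variable, not a stated trigger, and skin irritation appears in section H [v] as a possible ground for excluding an infant. As shown, the bias may be nil or reversed.
- **Single-device removals may be few.** An assistant observes attachment so that errors can be corrected, and is on hand for complications. The sentence just before the removal rule has all monitoring stop if the guardian, nurse or assistant is concerned, which affects all devices alike. The section does not say what separates that case from removal of one device, and the two sentences should be reconciled. The number of one-sided removals remains unknown.
- **Limits of agreement are not affected in the same way.** A reader might infer that removal could also distort a ranking of the devices by their limits of agreement. Among the test devices, only NTM is described as giving a continuous numerical reading, so there is no second set of limits to rank against. The point concerns hypothermia classification.

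It would also be too strong to say that removals will go unreported. Hourly entries are required from all monitors, so gaps should show on the forms, and a comments log exists. What is missing is a specified record and report.

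**Conclusion.** The plan allows the tools to be compared on different infant-hours and provides neither a matched comparison nor a specified record of removals. Whether this biases the comparison depends on whether removal is related to measurement difficulty, which the documents do not settle.

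Under the main assumed values (sensitivity 0.90 and 0.60, half of the difficult hypothermic hours lost), the false advantage is about 3 to 5 points. It is nil if removal is unrelated to error. These figures show the mechanism and are not a forecast. They also cannot be set against sampling error, because the number of hypothermic hours and the correlation within an infant are not given.

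This is a worthwhile, inexpensive improvement to the analysis. It does not undermine the assessment of each device against the gold standard, and it is no criticism of the removal rule.

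**What to change.** Leave the removal rule as it is, and make three additions before data collection starts.

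1. **Analysis (section H [vii]).** Keep each device's result against the gold standard on all its available hours. Add a comparison for each of the three device pairs on hourly hypothermia classification, the measure that all three share; for NTM the hourly state follows from its reading or light. Restrict each pair to infant-hours in which both devices and the gold standard were in place. Report the differences in sensitivity and specificity with intervals that allow for clustering by infant, for example by resampling infants. Working pair by pair, rather than requiring all three devices, means that removal of one device does not discard valid hours for the other two.
2. **Recording (section H [vi]).** Add device, time and reason for each removal, and time of any reapplication, to the existing monitoring form.
3. **Reporting (section H [viii]).** Show removals, reasons and hours lost per device beside the accuracy results, and state that common-hours results describe only infants, and hours, in which both devices were kept on.

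The cost is an extra entry on the form, an analysis filter and one table. The downside is that some hours drop out of the head-to-head comparison, with some loss of precision; the all-hours results remain.
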